A total of 38 participants were enrolled, with randomisation into two groups (n=17 experimental, n=17 control). Sample size was determined using power analysis for an independent t-test, accounting for a 10% dropout rate.

Statistical Analysis

Data will be analysed using SPSS v25.0. Statistical tests include independent t-tests, paired t-tests, and effect size calculations (Cohen's d, Hedges' g). Significance is set at $p<0.05$.

Ethical Approval

The study was approved by the institutional ethics committee on 27 December 2024 (Nr. SSV6-114). All participants provided written informed consent.

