Statistical Analysis Plan (SAP)

Official Title:

Clinical Evaluation of Kinesio Taping Outcomes in Stage II Cellulite: A Pilot Randomised Controlled Trial

NCT Number:

NCTXXXXXXX

Document Date:

September 16, 2025

Sponsor/Collaborator:

Klaipėda State University of Applied Sciences (Klaipėdos valstybinė kolegija)

1. Introduction

This Statistical Analysis Plan (SAP) describes the planned analyses for the pilot randomised controlled trial evaluating the effects of kinesio taping on women with stage II cellulite. The SAP defines analysis populations, statistical methods, and reporting conventions in accordance with best practice guidelines.

2. Study Objectives

Primary Objectives:

- To evaluate the effect of kinesio taping on dermis density.
- To evaluate the effect of kinesio taping on low echogenic band (LEB) thickness.

Secondary Objectives:

- To assess changes in thigh circumference, body composition, cellulite stage, and skin moisture.
- To explore persistence of effects at 4 weeks post-intervention.

3. Study Design

This is a two-arm, open-label, parallel-assignment randomised controlled trial with an experimental group (kinesio taping) and a control group (no intervention).

4. Analysis Populations

The primary analysis will be conducted on the intention-to-treat (ITT) population, including all randomised participants who completed at least baseline and one follow-up measurement. Per-protocol analyses may be conducted excluding participants with major protocol deviations.

5. Endpoints

Primary Endpoints:

- Change in dermis density (baseline to 4 weeks).
- Change in LEB thickness (baseline to 4 weeks).

Secondary Endpoints:

- Change in thigh circumference, body composition, cellulite stage, and skin moisture (baseline to 4 weeks and 8 weeks).
- Persistence of dermal changes at 8 weeks.
- Exploratory regression of baseline fat percentage on changes in adiposity and cellulite measures.

6. Statistical Methods

Descriptive statistics (mean, standard deviation, median, interquartile range) will be provided for all continuous variables. Frequencies and percentages will be presented for categorical variables.

Comparisons between groups will be performed using independent samples t-tests (or Mann-Whitney U test if data are non-normal). Within-group changes will be assessed using paired t-tests (or Wilcoxon signed-rank test). Effect sizes (Cohen's d, Hedges' g) will be reported to quantify magnitude of differences.

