For secondary analyses, linear regression will be used to explore associations between baseline body fat percentage and changes in adiposity outcomes. Significance will be set at $p < 0.05$.

7. Handling of Missing Data

Missing data will be evaluated for randomness. If $<5\%$ missing, analyses will be conducted using complete cases. If $>5\%$, multiple imputation methods will be considered. Sensitivity analyses will be performed to assess robustness.

8. Interim Analysis

No interim analyses are planned due to the small sample size and short study duration.

9. Statistical Software

All analyses will be conducted using SPSS version 25.0. Supplementary analyses may be performed using R version 4.3 or later.

10. Reporting

Results will be reported in accordance with CONSORT guidelines. Tables and figures will be used to illustrate changes in primary and secondary outcomes. Effect sizes, confidence intervals, and p-values will be reported.

11. Ethical Considerations

All analyses will be performed on de-identified data. Analyses will adhere to ethical standards and respect participant privacy.

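### SAP 6 lets the outcome data choose between a t-test and a rank test with no stated trigger, so the hypothesis tested for each endpoint is not fixed in advance.

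*SAP*

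**What the plan says.** SAP 6 gives the between-group rule: "Comparisons between groups will be performed using independent samples t-tests (or Mann-Whitney U test if data are non-normal". For change within each arm it says: "Within-group changes will be assessed using paired t-tests (or Wilcoxon signed-rank test". The first choice depends on normality, with no test, threshold or variable named (change scores, each arm, or residuals). The second has no stated condition at all.

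The effect measure does not depend on the test: "Effect sizes (Cohen's d, Hedges' g) will be reported to quantify magnitude of differences". SAP 10 is equally unconditional: "Effect sizes, confidence intervals, and p-values will be reported". Neither section says what quantity the confidence interval is for.

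SAP 5 defines both primary endpoints as changes from baseline to 4 weeks and names no population summary, such as a difference in means. The protocol's Statistical Analysis section mentions only parametric tests: "Statistical tests include independent t-tests, paired t-tests". Its Sample Size section bases the number on an independent t-test and gives the arm sizes: "A total of 38 participants were enrolled, with randomisation into two groups (n=17 experimental, n=17 control".

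**The concern.** The t-test addresses a difference in means. The Mann-Whitney test addresses whether values in one arm tend to exceed those in the other. Under a pure location shift the two agree on what is being tested, but when the arms differ in shape they do not. Because the SAP names no target quantity, the choice of test sets the hypothesis, and that choice is made after the outcome data are in.

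Three consequences follow. Dermis density and LEB thickness, or week 4 and week 8 of the same measure, may be tested by different methods. In the rank branch, the p-value and the standardised mean difference beside it describe different things and can point to different conclusions. And with no stated trigger, the analyst of an open-label trial can justify either test after seeing both.

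**Working it through.** **Inputs.** From the documents: 17 per arm; significance at 0.05 (two-sided assumed, as sidedness is not stated); endpoints are changes from baseline. Not in the documents, so assumed: the trigger (Shapiro-Wilk p<0.05 in either arm, or on pooled residuals), the outcome distributions, and the baseline/follow-up correlation.

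**The plan's own figure.** 17 + 17 = 34, and 34/(1 − 0.10) = 37.8, which rounds up to 38. The dropout step reproduces. The base of 17 per arm cannot be checked, because effect size, SD and power are not given. It would follow from a standardised difference of 1.0 at 80% power (exact t: 16.7 per arm; power at 17 is 80.7%), but those inputs are assumptions.

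**How often the switch fires (simulation, 17 per arm, 6,000 to 10,000 runs per case).**

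| Analysed values | Either-arm trigger |
|---|---|
| Exactly normal | about 10% (about 5% on pooled residuals) |
| Change scores from lognormal measurements, sigma 0.2 to 0.5, correlation 0.5 to 0.7 | about 13% to 39% |

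The normal case agrees with arithmetic: 1 − 0.95² = 0.0975. For two independent primary endpoints with normal data, at least one switches with probability 1 − 0.95⁴ = 0.185. Exactly one switches, so that the two are tested differently, with probability 2 × 0.0975 × 0.9025 = 0.176. Independence is a simplification.

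**Does the choice matter?** When both arms have the same shape, the two tests disagree on p<0.05 in 1.7% to 4.0% of null trials and in 5.7% to 14.4% of trials with a 1-SD shift. The range runs from normal to strongly skewed values.

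**Type I error.** With equal shapes, the mechanical rule gives 4.9% to 5.9% (Monte Carlo standard error about √(0.05 × 0.95/6000) = 0.3 points). Taking the smaller of the two p-values gives about 5% to 7%. With equal means and SDs but one skewed and one normal arm, P(X>Y) is 0.46 to 0.48. The rank null is then false although the mean difference is zero. The rule rejects in 6.3% to 8.0% of such trials, against 5.4% to 5.8% for a fixed t-test.

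**Power.** With normal data and an assumed 1-SD shift, power is 0.800 for the fixed t-test and 0.800 for the switching rule.

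**Precision of the proposed model.** With equal variances σ² at both visits and correlation ρ, the arm-effect variance is proportional to 2(1 − ρ)σ² for change scores and (1 − ρ²)σ² after baseline adjustment. The ratio is (1 + ρ)/2, which is 0.75 at ρ = 0.5 and 0.85 at ρ = 0.7: reductions of 25% and 15%.

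**The case against.** The case against is that this is a wording gap in a self-described pilot. The error rate barely moves, and power with normal data is the same with or without the switch. Where data are truly skewed, switching is partly the rule working as intended, and it can gain power for a location shift: at skewness 1, drawing the analysed values directly, 0.844 against 0.811 for the fixed t-test. Cohen's d and Hedges' g give a common scale in either branch. All of this stands. It limits the size of the point but does not supply the missing trigger or target.

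Four stronger readings are tempting, and the documents do not support them.

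- A reader might infer that a confidence interval for the mean difference exists only if the t-test is chosen. SAP 6 and SAP 10 make neither effect sizes nor intervals conditional on the test, and neither promises a mean-difference interval in the first place. The fault is that the interval's target is unnamed.
- A reader might expect the rank test to be triggered in most trials. Drawing the analysed values themselves as lognormal (sigma 0.4 to 0.5) gives 56% to 69%. But the endpoints are changes, which can be negative, and that skew is not mild (skewness 1.32 to 1.75).
- A reader might see a contradiction between the protocol's list of t-tests and the SAP's rank tests. The protocol's list is introduced as what the tests include, so it need not be exhaustive.
- A reader might suspect that the test was or will be chosen on the results. The protocol reports enrolment in the past tense, but nothing shows that outcome data had been examined.

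**Conclusion.** The point holds as a recommended improvement. The SAP has a data-driven choice of test with no trigger and no named estimand, and no other section closes the gap. The gain from fixing it is a defined target for each endpoint, less analyst discretion and better precision. It is not the correction of a materially inflated false-positive rate.

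The switching frequencies rest on a trigger and distributions that the documents do not give, so they illustrate scale and do not predict what this trial will do. The small effect on type I error applies when the arms have similar shapes; it is larger, up to 8.0%, in the most extreme unequal-shape case examined. The precision gain depends on the assumed correlation and equal variances.

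**What to change.** In SAP 6, delete the clause that replaces the t-test when normality is doubted. For each continuous outcome, pre-specify one linear model of the follow-up value on arm and baseline value, and report the adjusted mean difference, its 95% confidence interval and p-value. This keeps the change endpoint: with baseline in the model, analysing follow-up or change gives the same arm effect. State in SAP 10 that the interval is for this difference.

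Always report the Mann-Whitney test as a sensitivity analysis that does not replace the primary result. Name one method for within-group change in the same way. Keep a rank-based analysis for cellulite stage, which is ordinal. Align the protocol's Statistical Analysis section.

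Naming the t-test alone would remove the switch, but would forgo the precision gain. The model also supplies the estimate and standard error needed to pool results if the multiple imputation considered in SAP 7 is used.

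The cost is document wording and one sensitivity line per endpoint. Baseline is already measured, and there is no change to sample size, visits or data collection.

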Study Protocol

Official Title:

Clinical Evaluation of Kinesio Taping Outcomes in Stage II Cellulite: A Pilot Randomised Controlled Trial

NCT Number:

NCTXXXXXXX

Document Date:

September 16, 2025

Sponsor/Collaborator:

Klaipėda State University of Applied Sciences (Klaipėdos valstybinė kolegija)

Background

Cellulite is a common skin condition characterized by dimpling and uneven surface texture, primarily affecting women. It is associated with changes in the dermis and subcutaneous tissue, impaired microcirculation, and lymphatic congestion. Kinesio taping is a physiotherapy technique that may improve microcirculation and skin structure, but evidence for its effectiveness in cellulite is limited.

Objectives

The primary objective of this pilot randomised controlled trial is to evaluate the effects of kinesio taping on dermis density and low echogenic band (LEB) thickness in women with stage II cellulite. Secondary objectives include assessing changes in thigh circumference, body composition, cellulite stage, and skin moisture.

Study Design

This is a two-arm, parallel-assignment, open-label, randomised controlled trial.

Participants are allocated to either an experimental group (kinesio taping) or a control group (no intervention).

Participants

Eligible participants are women aged 18–45 years with stage II cellulite and normal body mass index (BMI). Exclusion criteria include pregnancy, edema, obesity, thrombosis, and skin infections.

Intervention

Experimental group participants receive kinesio taping once weekly for four consecutive weeks. Fan-shaped elastic tape is applied with 0–15% tension to the buttocks and thighs at standard anatomical points (gluteus maximus, posterior thigh, anterior thigh). Control group participants do not receive any intervention during the study period.

Outcome Measures

Primary Outcomes:

- Change in dermis density (measured by high-frequency ultrasound, DermaLab Combo 4).
- Change in low echogenic band (LEB) thickness (measured by ultrasound).

Secondary Outcomes:

- Change in thigh circumference (20 cm below the greater trochanter).
- Change in body composition (fat percentage, fat mass, fat-free mass, basal metabolic rate, total body water).
- Change in cellulite stage (Nürnberg-Müller Scale, Callegari Soft Plus).
- Change in skin moisture (Callegari Soft Plus device).

Sample Size

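### If change in fat percentage is an outcome of the exploratory regression on baseline fat percentage, its 5% test rejects too often, toward a negative slope, when nothing has changed

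*SAP*

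**What the plan says.** SAP section 6 states that "linear regression will be used to explore associations between baseline body fat percentage and changes in adiposity outcomes", and sets significance at the 5% level in the next sentence. SAP section 5 lists the same analysis among the secondary endpoints as "Exploratory regression of baseline fat percentage on changes in adiposity and cellulite measures". The two entries differ. Section 5 adds cellulite measures, which section 6 omits, and its wording reverses predictor and outcome.

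Neither section defines adiposity, names the outcomes, or mentions arm, an interaction or an analysis by arm. Neither chooses a time point, although section 5 defines the secondary endpoints at two: "Change in thigh circumference, body composition, cellulite stage, and skin moisture (baseline to 4 weeks and 8 weeks".

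The Protocol's Outcome Measures section includes "Change in body composition (fat percentage, fat mass, fat-free mass, basal metabolic rate, total body water". Fat percentage is therefore a change outcome of the trial and an obvious candidate for this regression. No document actually assigns it to the regression.

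**The concern.** If the outcome is change in fat percentage, the baseline reading is the predictor and is also subtracted to form the outcome. A woman whose baseline reading is too high by chance looks fatter at entry and appears to lose fat later. This produces a negative slope in taped and untreated women alike, with no real change in anyone. A significant result could then be reported as women with more fat having lost more.

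A separate matter concerns interpretation. Whatever the outcome, a slope pooled over both arms mixes taped and untreated women, and a slope in taped women alone has no comparator. Only the difference in slopes between arms bears on whether response to taping depends on baseline fat.

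**Working it through.** **Inputs.** From the documents: 38 enrolled, 17 + 17 = 34 in the two groups, 10% dropout allowance (Protocol, Sample Size); 5% level (SAP section 6), sidedness not stated and taken as two-sided. Assumed, because the documents give none: reliability R of a fat-percentage reading, from 0.80 to 0.99.

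**The plan's own figure.** The documents state no figure for this regression. The dropout step reproduces: 34 / 0.9 = 37.8, rounded up to 38.

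**Expected slope.** Let baseline b = T + e1 and follow-up f = T + e2, with true value T unchanged and errors independent. Scale var(b) to 1, so var(e1) = 1 − R.

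- Change = f − b = e2 − e1.
- cov(change, b) = −var(e1), so the expected slope = −(1 − R) = R − 1, whatever the follow-up error variance.
- With equal error variances, var(change) = 2(1 − R), and the correlation = −√((1 − R)/2).

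**Hand check at R = 0.95, N = 34.** Correlation = −√0.025 = −0.158. Fisher z: 0.1595 × √31 = 0.888. Lower tail: Φ(−1.96 + 0.888) = Φ(−1.072) ≈ 0.142. Upper tail: Φ(−2.848) ≈ 0.002. Total about 14.4%.

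**Simulation, no true change, equal error variances, N = 34, 10,000 trials per row.**

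| R | Expected slope | Rejection at 5% | Of which negative |
|---|---|---|---|
| 0.99 | −0.01 | 6.9% | 6.0% |
| 0.98 | −0.02 | 8.9% | 8.3% |
| 0.95 | −0.05 | 14.7% | 14.4% |
| 0.90 | −0.10 | 24.9% | 24.9% |
| 0.80 | −0.20 | 45.4% | 45.4% |

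Larger runs agree within simulation error.

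**Sensitivity.**

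- Sample size from 31 (34 × 0.9 = 30.6) to 38: about 14% to 16% at R = 0.95 and 23% to 28% at R = 0.90.
- One arm of 17: 7%, 9%, 14% and 24% at R = 0.98, 0.95, 0.90 and 0.80.
- True individual changes unrelated to baseline, SD 0.25 of the baseline SD: about 6% at R = 0.98 and 11% at R = 0.95. The slope is still R − 1, but the extra spread hides it.
- Follow-up error variance doubled or tripled at R = 0.90: about 18% and 14%.

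**Does the missing arm term cause it?** No. At R = 0.95 an arm main effect moves rejection only from 14.7% to 14.3%. With a true arm effect of 1 SD of change, the slope without an arm term stays at −0.05 (R = 0.95) and −0.10 (R = 0.90). The arm-by-baseline interaction rejects in 5.0% at R = 0.95.

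**Other outcomes** (own reliability 0.90, true values correlated 0.6 with fat percentage). If the baseline error is independent of fat-percentage error, the simple regression rejects in 5.0%. If the errors correlate 0.5 or 0.8, it rejects in 9.7% or 17.2%.

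**A trap in the remedy.** Suppose another outcome, with independent error, is analysed with its own baseline in the model. The interaction holds at about 5%. The slope on baseline fat percentage does not: at reliability 0.90 and true values correlated 0.9, with no true change, it averages 0.24 and rejects in 33% of trials.

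**The case against.** The analysis is labelled exploratory and promises only associations. That stands, and it caps the point at minor. Still, a 5% threshold is attached, and SAP section 10 says p-values will be reported.

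The premise is unconfirmed, because fat percentage is never named as an outcome of this regression. That also stands, so the inflation is conditional. The remedy starts by listing the outcomes.

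The size rests on an unknown reliability. This is correct: at 0.99 the excess is about two percentage points, and true individual change shrinks it further. The direction does not depend on the value chosen; the size does.

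The interaction answers a question the SAP does not pose, and answers it imprecisely. This is fair. Effect modification by baseline fat is not among the objectives in SAP section 2. The interaction is offered only where the simple test cannot be trusted, or as an option.

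A reader might infer three stronger claims that the documents do not support. One is that the missing arm term causes the false positives; the calculation shows otherwise, and silence about arm does not exclude it. Another is that the SAP presents the slope as response to taping; it does not. The third is that every outcome is affected; those with independent error are not.

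**Conclusion.** The concern holds in conditional form and is minor. If change in fat percentage is tested against baseline fat percentage as section 6 describes, the test is biased toward a negative slope when nothing changes. The excess over 5% is small at reliability 0.98 to 0.99 and large at 0.90 or below. The tabulated rates assume normal data, equal error variances and no true individual change; the documents cannot place this trial on that range. The inflation extends to other outcomes only as far as they share baseline error with fat percentage. The mismatch between SAP sections 5 and 6, and the limit on reading any single slope as a taping effect, need no assumption about reliability. The primary comparisons of dermis density and LEB thickness are untouched.

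**What to change.** Change the wording of SAP sections 5 and 6 as follows.

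- Align the two entries: same direction of regression, same outcomes (cellulite measures in or out), outcomes listed by name, time point stated.
- Do not test change in fat percentage, or in any outcome sharing its baseline error, against baseline fat percentage. For these, fit follow-up value on arm, baseline fat percentage and arm × baseline fat percentage, adding the outcome's own baseline if it is a different measure. Report only the interaction with its 95% CI, as exploratory.
- For outcomes with independent error, keep the simple regression of change on baseline fat percentage with arm added, and leave out the outcome's own baseline. If the interaction model with that baseline is fitted instead, test only the interaction, because its slope on baseline fat percentage is biased under no change.
- State that no slope on baseline fat percentage is a taping effect.

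No new data are needed. The cost is imprecision: with 17 per arm, the 95% CI half-width for the interaction is about 0.24 SD per SD at reliability 0.95 and 0.33 at 0.90. Power for a slope difference of −0.2 is about 39% and 22% to 23%. The interaction will rarely settle the question and should be reported with that caution.

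### Does the plan need to name the deciding test, and a rule for its two primary endpoints, before its results can be trusted?

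*SAP*

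**What the plan says.** SAP section 2 gives two primary objectives as separate items. The first is "To evaluate the effect of kinesio taping on dermis density"; the second has the same form for LEB thickness. SAP section 5 makes the change in each measure from baseline to 4 weeks a primary endpoint.

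SAP section 6 begins its inferential methods with "Comparisons between groups will be performed using independent samples t-tests", with Mann-Whitney as the fallback. The next sentence is "Within-group changes will be assessed using paired t-tests (or Wilcoxon signed-rank test". After a sentence on regression comes the only significance level in the SAP: "Significance will be set at $p < 0.05". The protocol's Statistical Analysis paragraph treats the methods in the same unranked way ("Statistical tests include independent t-tests, paired t-tests, and effect size calculations") and sets the same level.

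Three other statements bear on the reading:

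- Protocol, Intervention: "Control group participants do not receive any intervention during the study period".
- Protocol, Sample Size: "Sample size was determined using power analysis for an independent t-test".
- Both titles call the trial a pilot.

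SAP section 4 assigns a population to the primary analysis. No section assigns it a test, and none states a rule for combining the two endpoints.

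**The concern.** There are two separate worries.

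The first is the contrast. A paired test in the taping arm makes no use of the control group. Anything that moves both arms alike, such as season, measurement practice or habits during the study, can make it significant when taping does nothing. SAP section 10 promises p-values, so paired and between-group p-values on the same primary endpoints could stand side by side with no stated ranking. A reader could take the wrong one as evidence of effect.

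The second is multiplicity. With two primary endpoints and one threshold, a report that declared the trial positive because either endpoint reached significance would not have a 5% error rate. The SAP does not rule that claim out.

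If both doors were open, the false-positive rate of the headline conclusion could be well above the nominal level.

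**Working it through.** **Inputs from the documents.** 38 enrolled, 17 in each group, 10% dropout allowance, independent t-test as the sizing basis (Protocol, Sample Size); threshold 0.05; two primary endpoints.

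**Inputs assumed, because the documents give none.** Two-sided t-tests; 17 analysed per arm; equal drift of 0 to 0.5 SD of change in both arms; correlation of 0 to 0.9 between endpoints; standardised effect d of 0.8 or 1.0.

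**The plan's own figure.** 17 + 17 = 34, and 34/0.9 = 37.8, which rounds up to 38, so the dropout step reproduces. The base of 17 cannot be checked, since no effect size, power or sidedness is given. At two-sided 0.05 and 80% power it corresponds to d of about 0.99.

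**Within-arm test under shared drift, no taping effect.** The paired statistic is noncentral t with 16 df and noncentrality drift × √17. At 0.3 SD that is 0.3 × 4.12 = 1.24; at 0.5 SD it is 2.06.

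| Drift (SD) | Taping-arm paired test significant | Between-group test significant |
|---|---|---|
| 0 | 5.0% | 5% |
| 0.1 | 6.7% | 5% |
| 0.2 | 12.1% | 5% |
| 0.3 | 21.4% | 5% |
| 0.5 | 49.1% | 5% |

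The last column is flat because equal drift cancels in the difference between arms (simulated 4.9% to 5.1%). Inferring an effect because taping is significant and control is not would be wrong about 17% of the time at 0.3 SD and 25% at 0.5 SD.

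**Two endpoints, between-group tests, no effect on either.**

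- Either-endpoint claim, independent endpoints: 1 − 0.95² = 9.75%. Simulated at correlation 0.5 and 0.9: 9.1% and 7.1%.
- Counting only false claims of benefit: 1 − 0.975² = 4.9%, then 4.5% and 3.5%, against 2.5% for one test.
- Each objective concluded separately: 5% each, with nothing to adjust.

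**What a formal adjustment would cost.** Single-endpoint power uses noncentral t with 32 df and noncentrality d × √(17/2).

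| | d = 1.0 | d = 0.8 |
|---|---|---|
| Unadjusted, one endpoint | 80.7% | 61.9% |
| Holm, effect on that endpoint only | about 71% | about 50% |
| Both endpoints required, correlation 0 to 0.9 | 65% to 76% | 38% to 55% |

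**Which claims does the plan make?** Set against these figures, the text supports neither troublesome claim. The objectives speak of the effect of taping, which in a trial with an untreated randomised control is a difference between arms. The within-group sentence speaks only of changes. The trial was sized on the independent t-test. The objectives are two separate items, and no sentence mentions overall success or success on either endpoint. The rows that apply to the plan as a sensible analyst would run it are therefore the 5% ones.

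**The case for a change.** The best case for a change is that a pointer is not a rule. Sizing on an independent t-test does not say which test decides. The pilot label does not make the tests descriptive either: the plan sets a threshold, cites a power analysis and states effect objectives, and nowhere calls its primary results exploratory or unadjusted. Stating the intended reading would cost no power and need no data.

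Much of this is true. The documents do not state the rule, the arithmetic above is sound, and a clarifying sentence would do no harm. It is also fair to read the 0.05 level as general although it follows the regression sentence, because the protocol sets the same level straight after its list of tests.

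What does not stand is the step from an unstated rule to a faulty analysis. With real drift, a significant paired test correctly rejects its own null of no change within the arm. It misleads only when read as a taping effect, and the plan does not ask for that reading. The 9.75% arises only from a claim that no passage proposes. The most natural clarification, separate conclusions drawn from the between-group tests, leaves every planned test and every p-value as it is. Holm, or requiring both endpoints, would alter results, but in a small pilot either is a debatable trade of power for protection against that same unmade claim. Whether within-arm changes carry p-values or only intervals is a matter of presentation.

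**Conclusion.** The gap is real, but it is one of missing detail that analysts fill sensibly, and it calls for no change. Read in line with its design, the plan tests each primary objective by a between-group comparison at 5%, and a change shared equally by both arms does not disturb that test. The larger figures (up to 49% for the paired test; 7.1% to 9.75% two-sided, or 3.5% to 4.9% for false benefit, for an either-endpoint claim) belong to conclusions the documents do not propose.

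All of these figures rest on assumed drift, correlation and effect size, on t-tests rather than the rank alternatives the SAP allows, and on 17 analysed per arm. The protocol leaves unclear whether 17 is before or after dropout; at 15 per arm, single-endpoint power would be 75% at d = 1.0 and 56% at d = 0.8. None of this alters the conclusion, which depends on what the plan claims rather than on the size of these rates. It would be different if a report argued efficacy from the taping arm alone, or declared overall success on whichever endpoint was significant. That would be a fault of the report.

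### SAP 6 puts 18 to 20 secondary between-arm comparisons under one unadjusted 0.05 threshold, so about one chance significant difference is expected if taping has no effect

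*SAP*

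**What the plan says.** SAP 6 closes with a single threshold: "Significance will be set at" p < 0.05. It follows directly after the sentence on secondary analyses and carries no exemption. The protocol's Statistical Analysis section repeats the same level. For the tests themselves, SAP 6 says "Comparisons between groups will be performed using independent samples t-tests (or Mann-Whitney U test if data are non-normal").

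SAP 5 lists as secondary endpoints "Change in thigh circumference, body composition, cellulite stage, and skin moisture (baseline to 4 weeks and 8 weeks") and "Persistence of dermal changes at 8 weeks". The protocol's Secondary Outcomes break one of these domains into five variables: "Change in body composition (fat percentage, fat mass, fat-free mass, basal metabolic rate, total body water"). They also name two instruments, a clinical scale and a device, for cellulite stage.

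Neither document contains a multiplicity adjustment, a testing order, or a statement that secondary p-values are descriptive. Among the endpoints in SAP 5, only the regression on baseline fat percentage is called exploratory. SAP 2 also words the persistence objective as exploratory. SAP 10 says that effect sizes, confidence intervals and p-values will be reported.

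**The concern.** The plan labels its endpoints primary and secondary but gives both the same decision rule. A 5% threshold applied once has a known error rate. Applied separately to some twenty outcomes and visits, it makes a chance result more likely than not if the tests are independent.

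The trial is open-label, has an untreated control and has 17 women per arm. If the primary endpoints were negative, nothing in the plan would prevent an isolated result, say skin moisture or total body water at one visit, from being presented as an effect of taping. The planned effect sizes would not expose it: with arms this small, any result that reaches significance also has a large observed effect size.

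The point concerns the secondary family only. It does not bear on how the two primary endpoints are concluded.

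**Working it through.** The documents state no error rate for the secondary family, so there is no figure of the plan's own to reproduce. The only stated rate is 0.05 per test.

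**Inputs**
- Level per test: 0.05 (SAP 6; Protocol, Statistical Analysis). Sidedness is not stated. Two-sided testing is assumed, which puts 0.025 in the direction of benefit.
- Thigh circumference: 1 variable, "Change in thigh circumference (20 cm below the greater trochanter").
- Body composition: 5 variables (Protocol, Secondary Outcomes).
- Cellulite stage: 1 variable, or 2 if the scale and the device are analysed separately.
- Skin moisture: 1 variable.
- Time points for these: weeks 4 and 8 (SAP 5).
- Dermis density and LEB thickness as secondary endpoints: 2 variables at week 8 only (SAP 5).
- Arm size: 17 per arm (Protocol, Sample Size).

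**Step 1: count the between-arm tests**
- One cellulite measure: (1 + 5 + 1 + 1) × 2 + 2 = 18.
- Two cellulite measures: (1 + 5 + 2 + 1) × 2 + 2 = 20.

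The paired within-group tests and the regression fall under the same threshold but are not in this count.

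**Step 2: expected number of chance results if taping has no effect**
- Either direction: 18 × 0.05 = 0.9; 20 × 0.05 = 1.0.
- Benefit only: 18 × 0.025 = 0.45; 20 × 0.025 = 0.50.

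These expectations do not depend on correlation. The second pair is also the upper bound on the chance of at least one significant benefit: 45% or 50% under any dependence.

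**Step 3: chance of at least one, independent tests**

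| Tests | Either direction | Direction of benefit |
|---|---|---|
| 18 | 1 − 0.95^18 = 60.3% | 1 − 0.975^18 = 36.6% |
| 20 | 1 − 0.95^20 = 64.2% | 1 − 0.975^20 = 39.7% |

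**Step 4: correlated tests**

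The documents give no correlations, so these are assumed. Null trials were simulated with 17 per arm and two-sided t-tests on 32 degrees of freedom.
- With correlations of 0.5 to 0.9 within body composition, 0.1 to 0.3 between other variables and 0.5 to 0.8 between visits (20,000 trials per scenario), the chance of any significant difference was 37% to 53% for 18 tests and 41% to 57% for 20.
- With 0.3 to 0.9 within body composition, 0 to 0.2 elsewhere and 0.3 to 0.8 between visits (40,000 trials per scenario), it was 39.6% to 59.3% for 18 tests and 41.5% to 63.2% for 20. In the direction of benefit it was 20.7% to 35.9% and 21.8% to 38.7%.

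Taken together: roughly 37% to 63% for either direction and 21% to 39% for benefit.

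**Step 5: week 4 alone**

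If every week-8 comparison is set aside as exploratory, 8 or 9 tests remain. Under independence:
- Either direction: 1 − 0.95^8 = 33.7%; 1 − 0.95^9 = 37.0%.
- Benefit: 1 − 0.975^8 = 18.3%; 1 − 0.975^9 = 20.4%.

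**Step 6: how a chance result would look**

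The smallest observed standardised difference that reaches p < 0.05 with 17 per arm is t(0.975, 32) × √(2/17) = 0.70 SD. A chance finding would therefore be reported with an effect size of at least that.

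**The case against.** The strongest reply is that this is a pilot, that primary and secondary endpoints are separated in both documents, and that no rule turns one secondary p < 0.05 into a trial conclusion. Effect sizes and confidence intervals are already promised. On this view only a clarifying sentence is missing. That is largely right about the remedy, which is why the fix is wording and not a redesign. It does not remove the gap: the plan declares a significance level for these tests and says nothing about how a significant result is to be read.

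SAP 2's exploratory wording for persistence also counts. It can be read as covering 10 of the 18 (or 11 of the 20) comparisons, those at week 8. It does not say that their p-values are descriptive, and the week-4 tests alone still carry a 34% to 37% chance of a significant difference under independence.

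Two stronger readings are tempting and should be resisted. A reader might take 60% to 64% as the chance of falsely claiming a benefit. Those figures count differences in either direction. Benefit alone is 36.6% to 39.7% under independence and cannot exceed 45% to 50%. The higher figures would apply to benefit only if each test were one-sided at 0.05, which the documents do not say. A reader might also infer that SAP 10 gives secondary p-values the same standing as primary ones. It says only that p-values will be reported.

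Finally, the calculations treat every endpoint as a t-test. Cellulite stage is graded, all women enter at stage II, and SAP 6 allows a rank test, so with many ties the error rate for that endpoint may differ from 5%. This makes the figures approximate.

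**Conclusion.** The concern holds for the secondary family. The plan as written applies an unadjusted 0.05 rule to 18 to 20 secondary between-arm comparisons, and under no effect about 0.9 to 1.0 of them would be significant in one direction or the other. The chance of at least one is 60% to 64% under independence and roughly 37% to 63% under the assumed correlations. For benefit the figures are about 37% to 40% and roughly 21% to 39%, against 2.5% for a single two-sided test.

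The count and the expected number follow from the documents and the stated level. The probabilities also rest on two-sided testing and on correlations that the documents do not give. The benefit figures further assume that each variable has a favourable direction, and the documents define none for fat-free mass, basal metabolic rate or total body water. The change should be made because the present rule leaves secondary claims unprotected. The primary conclusions are unaffected.

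**What to change.** In SAP 6, and in the matching sentence of the protocol's Statistical Analysis section, limit the 0.05 significance rule to the between-arm comparisons of dermis density and LEB thickness at week 4. Then add wording such as:

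*Secondary endpoints at weeks 4 and 8, within-group changes and the regression are presented as estimates with 95% confidence intervals. Any p-values for them are unadjusted and descriptive, and none will be called statistically significant. The number of secondary comparisons made will be stated.*

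Naming the within-group tests and the regression matters, because otherwise a lone significant result could still come from them.

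The change needs no new data or participants and keeps the effect sizes and intervals that SAP 10 already promises. Its cost is that an isolated secondary p < 0.05 can no longer be presented as a finding; it can only inform the design of a later trial.
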